6.1.2. Secondary outcomes

- ★ Decrease in the rate of COPD exacerbations per study group at 12 months (end of the trial treatment) and 6 months after the trial's termination (follow-up).
- ★ Decrease in the severity of the COPD exacerbations. The severity of the exacerbations will be measured based on the consumption of healthcare resources (i.e., visits to the Emergency Department, hospitalizations, or consultations), as follows:
 - ICU hospitalization: 4 points.
 - Standard hospitalization: 3 points.
 - Emergency Department visit: 2 points
 - Consultation involving a change in the patient's usual treatment: 1 point.
- ★ Time elapsed between the start of the treatment and the first COPD exacerbation
- ★ Use of drugs (antibiotics, corticosteroids, etc). Drug consumption will be scored as follows:
 - Use of antibiotics: 1 point.
 - Use of inhaled corticosteroids: 2 points.
 - Use of systemic corticosteroids: 3 points.
 - Use of oxygen therapy: 4 points.
 - Use of mechanical ventilation: 5 points.
- ★ Number of hospitalizations due to COPD exacerbations.
- ★ Days of hospitalization due to COPD exacerbations.
- ★ Number of visits to the Emergency Room.
- ★ Number of unscheduled medical consultations due to COPD exacerbations.
- ★ Health-related quality of life, as determined by an adapted version of the specific CAT test.
- ★ Healthcare expenditure resulting from resource consumption during episodes of COPD exacerbations occurring during the trial period.
- ★ Variations (change between the baseline level and months 0, 3, 6, and 12, as well as in comparison with the placebo) in the following immunological parameters in the patients participating in the immunological substudy (N = 60) and/or those of the subgroup of the induced sputum study (N = 20) (between month 0 prior to the administration of the vaccine and month 12).

In the case of patients participating in the IMMUNOLOGICAL SUBSTUDY (n = 60), changes in the below parameters will also be assessed during the randomization visit (visit 1) and the visits corresponding to months 3, 6, and 12:

- The specific humoral response [REDACTED]
- The in vitro proliferative response of specific T cells [REDACTED]

In a subgroup of patients (n = 20) selected from the group of patients participating in the immunological substudy (n = 60), the following parameters will also be evaluated in samples of induced sputum at month 0 (visit 1) and month 12:

- ★ IgA response to Bactek antigens assessed using ELISA technique.
- ★ Proteomic studies using the iTRAQ technique.
- ★ Genetic micro-RNA profile.
- ★ Phenotypic markers of leukocyte populations.
- ★ Neutrophil function studies: phagocytosis (Phagotest) and bacteriophage capacity of neutrophils (oxidative burst).

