## 5. TRIAL DESIGN

### 5.1. Description of the Primary and Secondary Outcome

- **Primary outcome:**

- The primary efficacy outcome is a decrease in the mean number of COPD exacerbations. A clinical diagnosis of an exacerbation according to the GOLD definition will be considered; that is, an event occurring throughout the natural course of the disease, characterized by a change of acute onset, beyond the daily variability, in the patient's dyspnea, cough, and/or expectoration, which may require a change in the patient's usual medication.

- **Secondary outcomes:**

- Decrease in the rate of COPD exacerbations per study group at 12 months (end of the trial treatment) and 6 months after the trial's termination (follow-up).
- Decrease in the severity of the COPD exacerbations. The severity of the exacerbations will be measured based on the consumption of healthcare resources (i.e., visits to the Emergency Department, hospitalizations, or consultations), as follows:
  - ICU hospitalization: 4 points.
  - Standard hospitalization: 3 points.
  - Emergency Department visit: 2 points.
  - Consultation involving a change in the patient's usual treatment: 1 point.

[name]  
Traductor-Intérprete Jurado de INGLÉS  
Nº 9971

- Time elapsed between the start of the treatment and the first COPD exacerbation.
- Use of drugs (antibiotics, corticosteroids, etc). Drug consumption will be scored as follows:
  - Use of antibiotics: 1 point.
  - Use of inhaled corticosteroids: 2 points.
  - Use of systemic corticosteroids: 3 points.
  - Use of oxygen therapy: 4 points.
  - Use of mechanical ventilation: 5 points.
- Number of hospitalizations due to COPD exacerbations.
- Days of hospitalization due to COPD exacerbations.
- Number of visits to the Emergency Room.
- Number of unscheduled medical consultations due to COPD exacerbations.
- Health-related quality of life, as determined by an adapted version of the specific CAT test.
- Healthcare expenditure resulting from resource consumption during episodes of COPD exacerbations occurring during the trial period.
- Variations (change between the baseline level and months 0, 3, 6, and 12, as well as in comparison with the placebo) in the following immunological parameters in the patients participating in the immunological substudy (N = 60) and/or those of the subgroup of the induced sputum study (N = 20) (between month 0 prior to the administration of the vaccine and month 12).

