#### **5.6. Description of the Subject “Termination Criteria” and “Discontinuation Criteria” During the Entire Trial or Parts of It**

The trial shall end with the trial's database lock.

Subjects may temporarily discontinue the treatment for 7 to 14 days in any of the following cases:

- Severe or very severe COPD exacerbation.

Acute exacerbations will be graded according to the following scale:

1. Mild (home care with or without contact with the subject's doctor).
2. Moderate (requiring a visit to the Emergency Department).
3. Severe (requiring hospitalization).
4. Very severe (requiring intubation and mechanical ventilation).

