## 8. EFFICACY ASSESSMENT

### 8.1. Specification of Efficacy Parameters

- **Primary outcome:** the number of COPD exacerbations due to infectious episodes diagnosed by the clinician in charge.
- **Secondary outcomes:**
  - Rate of COPD exacerbations per patient included in the study.
  - Decrease in the severity of the COPD exacerbations.
  - Time elapsed between the start of the treatment and the first COPD exacerbation.
  - Use of drugs (antibiotics, corticosteroids, etc).
  - Number of medical consultations due to COPD exacerbations.
  - Number of hospitalizations due to COPD exacerbations.
  - Days of hospitalization due to COPD exacerbations.
  - Number of visits to the Emergency Department resulting or not in hospitalization.
  - Health-related quality of life, as determined by an adapted version of the specific CAT test.
  - Ratio between the number of COPD exacerbations and the healthcare expenditure resulting from resource consumption during episodes of COPD exacerbations occurring during the trial period.

- Variations (change between the baseline level and months 0, 3, 6, and 12, as well as in comparison with the placebo) in the immunological parameters described in page 63.
- Safety outcomes:
  - ~ Overall rate, severity, and relationship of any adverse event per administration and patient.
  - ~ Assessment of local tolerability (tissular reactions in the administration site).
  - ~ Changes in standard laboratory parameters (serum chemistry and hematology).

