6.1.1. Primary outcome

The primary efficacy outcome is a decrease in the mean number of COPD exacerbations. A clinical diagnosis of an exacerbation according to the GOLD definition will be considered; that is, an event occurring throughout the natural course of the disease, characterized by a change of acute onset, beyond the daily variability, in the patient's dyspnea, cough, and/or expectoration, which may require a change in the patient's usual medication.

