7.4.1. Primary Efficacy Analysis

The rate of exacerbations per patient and the severity of these exacerbations will be compared using the chi-square test or Fisher's exact test. The relative risks will be estimated together with their 95% CI and median or Mann-Whitney tests. The number needed to treat (NNT) or number of events prevented per treatment will be estimated.

The rate of episodes occurred over time will be calculated, and the hazards ratio (HR) will be estimated together with its 95% CI following a Cox proportional-hazards model. The NNT (number of patients that need to be treated to avoid an event) will also be estimated.

Poisson model with robust estimation of incidence density will be used to include covariates in the model.

Poisson model assumes that the response variable is a count variable (number of exacerbations) and each subject has the same length of observation time. If the observation time for subjects varied, the Poisson model would need to be adjusted to account for the varying length of observation time per subject. In this case a Stata exposure option, *exposure(varname)*, will be used where *varname* corresponds to the length of time an individual was followed to adjust the Poisson regression estimates. Also, Poisson model assumes that the dependent variable is not over-dispersed and does not have an excessive number of zeros (in whose case Negative Binomial and Zero-inflated models would be preferred).

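### The severity test compares only the exacerbations that occurred, so it can mislead in either direction if the vaccine prevents mild and severe events unequally; separately, the score has no level below a treatment-changing consultation

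*SAP*

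**What the plan says.** Severity is a secondary outcome in protocol 5.1 and SAP 6.1.2, introduced in the protocol as "Decrease in the severity of the COPD exacerbations". The SAP states that "The severity of the exacerbations will be measured based on the consumption of healthcare resources". Four levels follow: 4 points for an ICU stay, 3 for a standard admission, 2 for an emergency visit, and last "Consultation involving a change in the patient's usual treatment: 1 point".

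The analysis stands in SAP 7.4.1, under the primary efficacy heading, and in the same terms in protocol 10.1: "The rate of exacerbations per patient and the severity of these exacerbations will be compared using the chi-square test or Fisher's exact test".

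The exacerbations being counted are defined more widely than the score. SAP 6.1.1 describes an acute change in symptoms "which may require a change in the patient's usual medication", so a medication change is possible but not required. Protocol 5.6, in a different four-grade scale used for temporary interruption of treatment, has as its lowest grade "Mild (home care with or without contact with the subject's doctor".

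Neither document gives exacerbation-free patients a severity value, names the unit of analysis, or says how several levels within one episode, or several episodes in one patient, are combined.

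**The concern.** There are two separate problems.

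**Conditioning on the event.** A severity table built from events leaves out patients who had none. Whether a patient has an event, and which kind, is what the vaccine is meant to change. The two sets of events are therefore no longer protected by randomisation, and the comparison answers how severe the remaining events are, not whether patients fared better. If low-score events are prevented more than high-score ones, the remaining mix looks worse even though every category fell. Patients can also contribute several events, which the chi-square and Fisher tests would treat as independent.

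**Gap in the scale.** An exacerbation seen without a treatment change, or managed at home, can meet the definition for the count and still have no severity value. Whether such events are dropped or set to 0 is left open, and so is whether an episode that passes through several levels takes the highest or something else. These choices could be made after the data are seen.

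At stake is the interpretation of one secondary outcome, whose test is placed in the SAP beside the primary analysis.

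**Working it through.** The documents give no severity figure to reproduce and no severity mix, so this is an illustration.

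**Inputs**
- Prior rate: 3 events a year, an assumption in line with the entry criterion of at least three moderate exacerbations (SAP 5.2.1).
- Planned decreases of 30% on placebo and 60% on active (SAP 7.1.1): 3 × 0.70 = 2.1 and 3 × 0.40 = 1.2 events a year.
- Placebo mix, assumed: 65% at 1 point, 20% at 2, 15% at 3. Yearly rates are 1.365, 0.42 and 0.315.
- 70 evaluable patients per arm, assumed; 90 less 20–25% dropout is 72 to 67.5.

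**Formulas.** With rate r_k at score s_k, points per patient-year = Σ s_k r_k, and mean points per event = Σ s_k r_k / Σ r_k. If every r_k is multiplied by the same factor, that factor cancels from the mean.

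**Placebo.** 1.365 + 2 × 0.42 + 3 × 0.315 = 3.15 points; 3.15 / 2.1 = 1.50 per event.

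**Active, 1-point events cut 50% and higher ones 25%.** Rates 0.6825, 0.315, 0.23625, total 1.23375. Points 0.6825 + 0.63 + 0.70875 = 2.02; 2.02125 / 1.23375 = 1.64 per event. Expected events at 70 per arm are 95.6/29.4/22.1 against 47.8/22.1/16.5: chi-square 2.15 on 2 df, p about 0.34.

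| Pattern on active | Mean per event (placebo 1.50) | Points per patient-year (placebo 3.15) | Chi-square p |
|---|---|---|---|
| All levels cut 43% | 1.50 | 1.80 | 1.0 |
| 1-point cut 50%, higher cut 25% | 1.64 | 2.02 | 0.34 |
| 1-point cut 25%, higher cut 50% | 1.38 | 1.92 | 0.37 |
| Only 0.42 one-point events prevented | 1.63 | 2.73 | 0.35 |
| Whole reduction to 1.2 from 1-point events | 1.88 | 2.25 | 0.0006 |

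The per-event mean does not track burden. The first row has the largest fall in points (43%) and shows no severity effect. The second and third have similar falls (36% and 39%) and point in opposite directions. The last row needs a 66% cut in 1-point events (1.365 to 0.465) and none at higher levels. Its p also assumes independent events: dividing the chi-square of 14.9 by an assumed variance inflation of 1.5 to 2 gives 0.007 to 0.024.

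**Adding home-managed events.** Three assumed placebo mixes (home/1/2/3/4 points): 40/40/10/8/2%, 25/45/15/12/3% and 10/50/20/17/3%, at 2.1 events a year.
- Mean per scored event on placebo: 1.53, 1.64, 1.70.
- Home and 1-point events cut 50%, higher cut 25%: 1.69, 1.80, 1.86, while points per patient fall from 1.93, 2.58, 3.21 to 1.24, 1.70, 2.15.
- Home and 1-point events cut 25%, higher cut 50%: 1.40, 1.49, 1.55.
- Only home events prevented, all of them: unchanged if they are unscored and left out. If they are scored 0, the mean rises from 0.92, 1.23, 1.53 to 1.53, 1.64, 1.70.

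So the treatment of unscored events, which the plan does not fix, can decide whether any difference appears.

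**The case against.** The strongest reply is that nothing in the documents says the vaccine would mainly prevent mild events. Protocol 3.4.2 cites experience with other bacterial preparations in which serious episodes and admissions fell. That evidence is from other products and does not settle the direction here, but it rules out presenting an apparent worsening as the expected result.

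Second, the gap in the scale may be narrow. Protocol 8.1 words the primary outcome as "the number of COPD exacerbations due to infectious episodes diagnosed by the clinician in charge", and protocol 5.2.1 asks subjects to attend whenever they develop symptoms of respiratory infection, so few counted events may lack all contact. This stands in part: an event diagnosed without a treatment change still has no score.

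Third, SAP 6.1.2 also plans admissions, hospital days, emergency visits and "Number of unscheduled medical consultations due to COPD exacerbations", where a fall in burden would show. These outcomes limit the harm but do not repair the severity test.

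Fourth, the text does not exclude a per-patient score. That is true, and it means the unit should be fixed in writing. A reader might also infer that an episode passing through consultation, emergency visit and ward scores the sum of those levels, above the top of the scale. No section says levels are added, and a categorical test suggests one level per episode. What can be said is that the rule is missing.

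**Conclusion.** The point holds, as a risk of a misleading direction in one secondary outcome. On its natural reading, the severity test conditions on a post-randomisation outcome and ignores repeated events within a patient. In the illustration, mean points per event rise from 1.50 to 1.64 while points per patient-year fall by 36%, with p about 0.34. The opposite pattern gives an apparent improvement (1.38), and equal prevention gives no change. The size depends on the assumed event rates and mix; the dependence on the pattern of prevention does not.

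A reader might infer that the vaccine will appear to worsen severity, or that a significant result against it is likely. The documents do not support either. A significant reversal appeared only when the whole planned reduction came from 1-point events. Nor can home-managed events cause the reversal if they are unscored and left out. The missing lowest level and the missing aggregation rule are separate defects of definition.

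**What to change.** In protocol 5.1 and 10.1 and SAP 6.1.2 and 7.4.1:

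1. Score each episode once, at the highest level reached.
2. Give counted exacerbations without a treatment-changing consultation a defined lowest level. If that level were 0, such an event would count the same as no event in a sum, so the value should be stated deliberately.
3. Compare arms in the ITT set on a per-patient basis over 12 months, with exacerbation-free patients at 0. Use either the summed score or per-patient event rates by severity level; choose one before database lock and state how shorter follow-up is handled.
4. Keep the per-event severity distribution as a descriptive table and remove its test.

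The cost is mainly wording. Healthcare use is already recorded at every visit, and the lowest level can be assigned to any counted exacerbation with no qualifying contact. The downside is that a summed score partly reflects the number of events, which is why the descriptive per-event table should stay beside it.

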Exacerbations are associated with a significant worsening in the patients' quality of life, and the degree of disability caused by this condition depends on the number of exacerbations experienced. Albeit with seasonal variations, exacerbations of COPD are a frequent cause of consultations in both primary care and hospital services, and represent 2% of all medical emergencies attended. Exacerbations of infectious nature account for 1.5% of all emergencies attended in the hospital and for 13.7% of all infections. Up to 40% of subjects treated for this cause in the Emergency Department require hospitalization. Approximately 4% of the general European population consults their general practitioner at least once a year due to experiencing a respiratory exacerbation, and 20% of these consultations correspond to subjects with COPD. In Spain, empirical antibiotic treatment is prescribed in over 90% of cases of respiratory exacerbation of COPD, although sputum microbiology is only studied in 5% of subjects. Penicillins, cephalosporins, and macrolides are the most widely used antibiotics for the treatment of exacerbations of chronic bronchitis and COPD in Spain, followed by quinolones.

Infection causes 75% of COPD exacerbations. Bacteria are responsible for half of these exacerbations of infectious etiology, which are mainly caused by *Haemophilus influenzae*, *Streptococcus pneumoniae*, *Moraxella catarrhalis*, and *Chlamydia pneumoniae*. However, in patients suffering from severe COPD presenting

with an exacerbation requiring mechanical ventilation, this infection might be caused by *Pseudomonas aeruginosa*. The rest of infectious exacerbations are caused by viruses, occasionally associated with bacteria, or exceptionally by other microorganisms.

In addition to directly affecting social and health resources consumption, any intervention that can reduce the incidence of COPD exacerbations can have a great impact on the morbidity and quality of life of the affected subjects. Because bacterial infections of the respiratory tract are a well-known risk factor for the onset of COPD exacerbations, prevention and appropriate treatment of these infections may represent an attractive modality for avoiding the development of exacerbations.

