**All subjects will start treatment with Bactek vs. placebo in a stable clinical condition.**

- The subjects shall attend study visits every 3 months and whenever they develop symptoms of respiratory infection.
- They must strictly record the number of days of oral or systemic antibiotic treatment required until the remission of their ailment (COPD exacerbation).
- The number of days of hospitalization required due to the severity of the clinical condition (COPD exacerbation both during and after the immunization [6 months]) will be strictly recorded until the patient's clinical symptoms resolve and they are discharged home in a stable clinical condition.
- The pre- and post-immunization quality of life will be recorded using the specific CAT survey.
- Baseline Visit (prior to the start of the treatment)

The baseline visit can take place 1-4 weeks before the start of the treatment (visit 1), and the following tests will be performed that day (Table 1):

- Informed consent.

- Inclusion and exclusion criteria.
- Demographic data (including residence data).
- Vital signs (body temperature [BT] and HR).
- Tobacco consumption (no. of cigarettes/day x no. of years/20).
- Medical history/complete examination (description of the abnormality).
- Measured exhaled CO.
- Collection of blood samples to perform the following tests:
  - ~ Hematology
  - ~ Serum chemistry
  - ~ Viral serology testing
  - ~ Immunological assessment

A blood sample of each patient will be collected during the baseline visit for the following:

- Determination of serum levels of IgG, IgA, and IgM. In patients with IgG levels <500 mg/dl or IgA levels <6 mg/dl, a determination of the IgG subclasses will be performed (nephelometry, Beckmann Coulter, USA) to rule out an immunodeficiency.
- Serum concentration of the anti-pneumococcal and anti-tetanus toxoid antibodies. An *in vivo* response study will also be performed in patients with low levels of antibodies in order to rule out an immunodeficiency in antibody

production.

- Spirometry.
- Recording of concomitant medication.
- Pregnancy test (for women of childbearing age).
- Recording of the consumption of healthcare resources.
- Subject's visual analog scale score.
- Investigator's visual analog scale score.
- Quality-of-life questionnaire.
- Comments.
- CRF review.

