7.4.2. Secondary Efficacy Analysis

The following variables will be analyzed to determine whether they follow a normal distribution: number of exacerbations, duration of the episodes, need for antibiotic therapy, number of hospital admissions, duration of the hospital admissions, immunological outcomes described in the trial design, quality of life, and direct costs.

These variables will be described together with their mean and standard deviation, or, in case of asymmetry, with their median and interquartile range. Differences between the means will be analyzed using Student's T test in the case of variables with a normal distribution and Mood's median test in the case of variables without a normal distribution. The absolute effect (difference in estimators) and its precision will be estimated with a 95% confidence interval (CI) in all cases.

The appearance of the first exacerbation will be studied at 3, 6, 12 months and whole study in the intention to treat (ITT) and per protocol (PP) sets and these same limits will be studied in the moderate and severe COPD populations. The appearance of any exacerbation at 3, 6, 12 months and whole study will be studied in the ITT and PP sets.

Number of exacerbations will be studied in the mild, moderate and severe COPD populations at 3, 6, 12 months and whole study. Number of exacerbations in the ITT and PP sets will be studied at 3, 6, and 12 months.

To compare the change in the immunological variables described in the trial design at 0, 3, 6, 12, and 18 months, an analysis of covariance will be performed, estimating the mean difference over time in both study groups.

The cost-benefit ratios in the study groups will be estimated together with their 95% CI, and compared using non-parametric tests.

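### The drug-use score has no counting unit, summation rule or named analysis; scored once per patient, it would lose about half of the expected relative effect

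*SAP*

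**What the plan says.** SAP 6.1.2, which matches Protocol 5.1, lists drug use as a secondary outcome: "Use of drugs (antibiotics, corticosteroids, etc). Drug consumption will be scored as follows". The points run from 1 to 5, for example "Use of antibiotics: 1 point" and "Use of systemic corticosteroids: 3 points". Neither document states the unit to which a point attaches, or a rule for summing points.

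SAP 7.4.2 does not mention the score. Its list of variables includes "need for antibiotic therapy, number of hospital admissions, duration of the hospital admissions", and antibiotic need is the only drug item there. Corticosteroids, oxygen and ventilation are not named. For every variable in the list the rule is: "Differences between the means will be analyzed using Student's T test in the case of variables with a normal distribution and Mood's median test", the latter when the distribution is not normal.

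The amount of antibiotic treatment is collected. Protocol 5.2.1 says of the subjects: "They must strictly record the number of days of oral or systemic antibiotic treatment required". The schedule (Table 1 in both documents) has antibiotic days at visits 1 to 6; Protocol 8.2 says visits 1 to 4. Both cover the 12 months of treatment. No analysis section refers to antibiotic days by name.

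SAP 7.4.1 describes a Poisson model with robust estimation, an exposure term for unequal follow-up, and a negative binomial alternative. It assigns these to the number of exacerbations only.

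**The concern.** Less antibiotic use is one of the advantages claimed for the product in Protocol 3.5, and drug use is a listed objective. Eligible patients have had at least three moderate exacerbations in the past year, or two with at least one hospitalization. Protocol 3.2 says that in Spain "empirical antibiotic treatment is prescribed in over 90% of cases of respiratory exacerbation of COPD". Most patients in both arms can therefore be expected to receive antibiotics at least once, and a real benefit would show mainly as fewer repeat courses.

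A measure of any use cannot show fewer repeat courses; a count of courses or days can. The SAP does not say which it intends. The choice could be made after the data are seen, between measures with very different power.

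**Working it through.** The documents give no power or effect figure for drug use, so there is none to reproduce. The 90 per group in SAP 7.1.1 concerns exacerbations and is used here only to set the number of evaluable patients.

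**Inputs**
- Fall in exacerbations: 60% active, 30% placebo (SAP 7.1.1).
- Exacerbations in the prior year: 3, from the inclusion criterion; range 2 to 5 (assumption).
- Share treated with antibiotics: 90%, the same in both arms (assumption, from Protocol 3.2).
- Evaluable per arm: 70 (assumption; 90 less 25% or 20% dropout gives 67.5 or 72).
- Dispersion k of counts between patients: 0 (Poisson), 0.5 and 1 (assumption). Two-sided 5% level (the plan does not state sidedness).

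**Courses per patient-year**
- Active: 3 × 0.4 × 0.9 = 1.08. Placebo: 3 × 0.7 × 0.9 = 1.89.
- Ratio 1.08/1.89 = 0.571, a 43% reduction.

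**Any use, if scored once per patient**
P(any) = 1 − exp(−μ) for k = 0, and 1 − (1 + kμ)^(−1/k) for k > 0.

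| k | Active | Placebo | Relative reduction | Share of the 43% kept |
|---|---|---|---|---|
| 0 | 66.0% | 84.9% | 22.2% | 52% |
| 0.5 | 57.8% | 73.6% | 21.4% | 50% |
| 1 | 51.9% | 65.4% | 20.6% | 48% |

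About 65% of placebo users would have two or more courses (k = 0: 0.56/0.849 = 0.66). Any use ignores those repeats. Over 2 to 5 baseline exacerbations, dispersion 0 to 2 and 90 to 100% treated, the share kept runs from 66% down to 25%.

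**Power, simulated with 70 per arm**

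| k | Any use, chi-square | Courses, Mood's median test | Courses, robust Poisson |
|---|---|---|---|
| 0 | 76% | 91% | 98% |
| 0.5 | 51% | 66% | 86% |
| 1 | 35% | 51% | 72% |

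The outer columns agree with closed-form results to within about two percentage points. For courses, the variance of the log rate ratio is (1/μ₁ + 1/μ₀ + 2k)/n. At k = 0 and n = 72 this is (0.926 + 0.529)/72 = 0.0202, so z = 0.560/0.142 = 3.94 and power = Φ(3.94 − 1.96) = 98%.

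The middle column is the reading on which antibiotic need is a count. Counts this small and skewed would be expected to fail the normality check and go to Mood's test, which only splits patients at the pooled median. A t test on courses stays close to the count model, so the loss comes from Mood's test. The simulation gives every patient a full year. Neither listed test allows for unequal follow-up, which a 20 to 25% dropout rate makes likely.

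**The case against.** Three stronger claims are tempting, and the documents do not support them.

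- **Five courses count the same as one.** The SAP never says that points are given once per patient. The severity score in the same list has the same form and concerns exacerbations, so scoring per exacerbation is at least as natural. Summed that way, nothing is lost through the unit.
- **Antibiotic need is a yes/no variable.** It stands among counts and durations, to be described by mean or median and compared as a quantity. It may mean the recorded number of days. That these days are collected and never used is therefore unproven; they are only not tied to an analysis by name.
- **Most of the effect is lost.** At three baseline exacerbations about half is kept, and more at two.

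SAP 7.1.9 also says that secondary endpoints will use relevant tests, which loosely covers the score. The full analysis set could exceed 70 per arm. The 90% figure describes Spanish practice, not this trial's patients. Courses in this model are thinned exacerbations, and the exacerbation count already has a count model in 7.4.1.

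All of this stands, and it makes the size of the loss conditional. It does not supply the missing unit, summation rule or specific analysis. Nor does it answer the weakness of Mood's test and the lack of a follow-up term on the quantitative reading.

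**Conclusion.** The drug-use score is not defined well enough to be analysed in only one way, and the one drug variable named for analysis is undefined and assigned to tests that do not suit it.

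- **Scored once per patient:** about half of the expected relative effect is lost at three baseline exacerbations (43% becomes 21 to 22%), with power of about 76/51/35% against 98/86/72% for courses.
- **Analysed as a count of courses:** the loss is smaller but remains under Mood's test, at about 91/66/51%, and follow-up time is ignored.

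These sizes rest on the assumed baseline rate, dispersion, treated share and 70 per arm. The definitional gap does not. The point concerns one secondary outcome; the primary conclusion does not change.

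**What to change.** In SAP 6.1.2 and 7.4.2, before unblinding:

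1. Replace the antibiotic-need variable with antibiotic courses and antibiotic days given for COPD exacerbations, per patient over 12 months. Add systemic-corticosteroid courses as a separate variable. Patients with none count as zero.
2. Analyse each with the robust Poisson or negative binomial model and the exposure term already in 7.4.1.
3. If the point score is kept, state that it is applied per exacerbation and summed over 12 months for each patient.
4. Report any use only as a simple proportion per arm.

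Antibiotic days and concomitant medication are already collected, so the cost is SAP wording and a little extra analysis, including a rule for deriving courses from the medication records.
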